9. STATISTICAL CONSIDERATIONS

Detailed methodology for summary and statistical analyses of the data collected in this study is outlined here and further detailed in a statistical analysis plan (SAP), which will be maintained by the Sponsor. The SAP may modify what is outlined in the protocol where appropriate; however, any major modifications of the primary endpoint definitions or their analyses will also be reflected in a protocol amendment.

9.1. Estimands and Statistical Hypotheses

For the primary endpoint, the null hypothesis is that there is no difference between fordadistrogene movaparvovec and placebo with respect to mean change from Baseline at Week 52 in the NSAA total score. The alternative hypothesis is that fordadistrogene movaparvovec is different from placebo with respect to mean change from Baseline at Week 52 in the NSAA total score.

The experiment-wise Type I error of $\alpha=0.05$ (two-sided) will be controlled using gatekeeping and fixed-sequence procedures for the primary and select secondary endpoints listed below. The hypotheses for the secondary endpoints are similar to those for the primary endpoint.

1. Change from Baseline at Week 52 in the 10 meter run/walk velocity.
2. Change from Baseline at Week 52 in the rise from floor velocity.
3. Number of skills either improved or maintained at Week 52 based on the individual items of the NSAA.
4. Number of skills gained at Week 52 based on the individual items of the NSAA.

If the null hypothesis for the primary endpoint is rejected, statistical testing proceeds to the hypotheses for the secondary endpoints; otherwise, formal statistical testing in the sense of controlling the experiment-wise Type I error stops and nominal p-values for secondary endpoints will be reported and interpreted accordingly.

The secondary endpoints will be tested in the order specified above. To maintain the study-wise type 1 error rate, the p-value boundary for these secondary endpoint analyses will be the same as the primary analysis as detailed in the Interim Analysis SAP.. If the null hypothesis for the first endpoint in the sequence is rejected, statistical testing moves to the next endpoint in the sequence. Statistical testing proceeds to subsequent endpoints in the sequence only if the null hypothesis for the previous endpoint is rejected. If a null hypothesis in the sequence is not rejected, formal statistical testing in the sense of controlling the experiment-wise Type I error is stopped for all endpoints later in the sequence and nominal p-values will be reported and interpreted accordingly.

The null hypothesis for the primary and secondary endpoints will be tested at Week 52 using the parameter and variance estimates from the MMRM model or the generalized mixed model described in [Section 9.4.1](#).

If either interim analysis is performed, a group sequential approach will be applied to the efficacy analyses to control Type I error across the interim analysis/analyses and the primary analysis. Specifically, a gamma family alpha-spending function with gamma parameter -1 will be used. Additionally, an assessment of futility (non-blinding) based on the primary endpoint will be made at each interim analysis, if performed, using a gamma family spending function with gamma parameter -4.

9.1.1. Estimands

Primary Estimand: This estimand will be the primary estimand and will be the difference in mean change from Baseline at Week 52 in the NSAA total score between fordadistrogene movaparvovec and placebo regardless of adherence to background and protocol-mandated glucocorticoid regimens (see [Section 6.5.1](#)) during the first 52 weeks:

- Population: Boys with a genetic diagnosis of DMD who are ambulatory and age ≥ 4 to <8 years;
- Variable: Change from Baseline at Week 52 in the NSAA total score;
- Death or loss of ambulation are identified as potential intercurrent events. Details on how these intercurrent events are handled in the analysis are provided in the SAP
- Population-level summary: Difference in mean changes from Baseline at Week 52 in the NSAA total score between fordadistrogene movaparvovec and placebo.

9.2. Sample Size Determination

A sufficient number of participants will be screened to achieve a total of approximately 99 participants in the FAS (see Section 9.3). Participants will be randomly assigned in a 2:1 fashion to Cohort 1 (approximately 66 participants) or Cohort 2 (approximately 33 participants) across the two strata (age <6 years and age \geq 6 years). This sample size is based on the primary efficacy endpoint of change from Baseline at Week 52 in the NSAA total score. The above sample size (assuming 3 participants will drop out of the study prior to Week 52) will provide 98% power to detect a treatment difference (fordadistrogene movaparvovec – placebo) of 3.0. These calculations are based on $\alpha=0.05$ (two-sided), a common standard deviation of 3.5 and using the normal approximation of the test statistic for the comparison between two means. Assuming both interim analyses will be performed (3 looks) and a gamma family alpha-spending function with gamma parameter -1 for efficacy will be used to control Type I error, the probability of crossing the boundary at the first interim analysis is 38%, at the second interim analysis is 78%, and at the primary analysis is 97%. A gamma family spending function with gamma parameter -4 will be used for the non-blinding futility boundary.

9.3. Populations for Analysis

For purposes of analysis, the following populations are defined:

Population	Description
Enrolled	All participants who sign the Informed Consent Document.
Randomly assigned to investigational product	All participants, excluding siblings, who were randomly assigned to Cohort 1 (initially fordadistrogene movaparvovec) or Cohort 2 (initially placebo).
Full Analysis Set (FAS) (through Week 52) ^a	All participants, excluding siblings and those meeting exclusion criterion 15, who were randomly assigned and received a single dose of IP on Day 1 (Year 1 Day 1). Participants will be analyzed according to the cohort to which they were randomized.
Safety Analysis Set (through Week 52)	All participants, including siblings and those meeting exclusion criterion 15, who were randomly assigned and received a single dose of IP on Day 1 (Year 1 Day 1). Participants will be analyzed according to the IP they actually received.
Efficacy Analysis Set (long-term)	All participants, including siblings, but excluding those meeting protocol exclusion criteria 15, who received a single dose of fordadistrogene movaparvovec (either at Year 1 or Year 2).
Safety Analysis Set (Cohort 2 delayed treatment)	All participants, including siblings, who received a single dose of fordadistrogene movaparvovec on Day 390 (Year 2 Day 1).
Safety Analysis Set (long-term)	All participants, including siblings and those meeting exclusion criterion 15, who received a single dose of fordadistrogene movaparvovec (either at Year 1 or Year 2).

^a Of note, per the PCD definition in Sections 4.1 and 9.5, the primary analysis will occur after at least 90 FAS participants complete Day 360 (Visit 19) or discontinue from the study prior to Week 52 if they had received Year 1 IP at least one year prior to the data cutoff.

9.4. Statistical Analyses

The SAP will be developed and finalized before database lock and will describe all planned statistical analyses including the participant populations to be included in the analyses and procedures for accounting for missing, unused, and spurious data. This section is a summary of the planned statistical analyses of the primary and secondary endpoints.

9.4.1. Efficacy Analyses

Endpoint	Statistical Analysis Methods
Primary	
Inferential testing for the primary analysis for the primary endpoint will be performed at $\alpha=0.05$ (two-sided).
 
Baseline NSAA total score is defined as the last non-missing NSAA total score collected prior to Year 1 IP administration.
 
Primary analysis: Change from Baseline at Week 52 in the NSAA total score will be analyzed using a mixed model repeated measures approach including visits through Week 52 where NSAA is assessed. The analysis will be based on the FAS (Regardless of adherence to glucocorticoid regimen) and missing data will not be explicitly imputed. The model will include fixed effects for treatment (class variable), visit (class variable), treatment by visit interaction, Baseline NSAA total score (continuous variable), Screening age (continuous variable), Baseline NSAA total score by visit interaction, and Screening age by visit interaction with an unstructured covariance matrix to describe the correlation among different visits from the same participant. Alternative covariance structures to address any issues with model convergence will be specified in the SAP. To test the null hypothesis, estimates at Week 52 of the mean changes from Baseline and 95% confidence intervals along with the mean treatment group difference, two-sided p-value, and two-sided 95% confidence interval for the mean difference will be provided.
 
Sensitivity analyses to assess the effect of missing data will be described in the SAP.

Secondary	
Inferential testing of the secondary endpoints will be performed as described in Section 9.1.
 
Baseline is defined as the last non-missing assessment collected prior to Year 1 IP administration.
 
The following endpoints will be analyzed using an analysis of covariance model including model terms for treatment group, Baseline (continuous variable), and Screening age (continuous variable).
 
• Change from Baseline in percent normal mini-dystrophin expression level in biceps brachii muscle biopsies at Day 360 using LC-MS assay.• Change from Baseline in percent of muscle fibers expressing mini-dystrophin in biceps brachii muscle biopsies at Day 360 as assessed by immunofluorescence. 
Change from Baseline at Week 52 in serum CK concentration will be analyzed using a mixed model repeated measures approach and a log transformation. The model fixed effects will be similar to those in the primary endpoint analysis and visits through Week 52 where serum CK concentration is assessed will be included.

Endpoint	Statistical Analysis Methods
	
The below two endpoints will be analyzed using a generalized mixed model assuming a binomial distribution and a logit link. The model terms will include treatment and Screening age (continuous variable).
 
Number of skills gained at Week 52 based on the individual items of the NSAA. For each individual item, a gained skill is defined as a score of 0 at Baseline and a score of 1 or 2 at Week 52.Number of skills either improved or maintained at Week 52 compared to Baseline based on the individual items of the NSAA. For each individual item, an improved or maintained skill is defined as a score of 0 at Baseline and a score of 1 or 2 at Week 52, a score of 1 at Baseline and a score of 2 at Week 52, a score of 1 at Baseline and a score of 1 at Week 52, or a score of 2 at Baseline and a score of 2 at Week 52. 
The following endpoints will be analyzed using a similar mixed model repeated measures approach as used for the primary analysis.
 
Change from Baseline at Week 52 in the 10 meter run/walk velocity;Change from Baseline at Week 52 in the rise from floor velocity;Change from Baseline at Week 52 in the Modified PODCI: Transfer and Basic Mobility Core Scale (Pediatric Parent);Change from Baseline at Week 52 in the Modified PODCI: Sports and Physical Functioning Core Scale (Pediatric Parent).
Exploratory	Analyses for the exploratory endpoints defined in Section 3.1 will be described in the SAP.

As a general rule, all efficacy analyses including analysis of the primary endpoint, secondary endpoints, and other endpoints will be conducted based on FAS participants regardless of adherence to background or protocol mandated glucocorticoid regimens during the first 52 weeks after study drug infusion, unless specified otherwise.

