Visit Number/Description	Screening	Baseline	Week 1, Day 1	Week 1, Day 2	Week 1, Day 4	Week 1, Day 6	Week 1, Day 7	Week 2, Day 8 & 9	Week 2, Day 10	Week 2, Day 14	Week 3	Week 4	Week 5	Week 6	Week 7	Week 9	Week 11	Week 13	Week 18	Week 35	Week 47	Week 52	
Visit Day	-90 to -30	-48 to -16	1	2	4	6	7	8 & 9	10	14	21	28	34	42	48	60	74	90	120	240	328	360	
Visit Window (\pm days)			0	0	0	0	0	0	0	1	1	1	1	3	3	3	3	7	7	14	7		

- n. **Banked biospecimens for genetics** are collected as described in [Section 8.7.2](#).
- o. **Open muscle biopsies** will be obtained in approximately the first 15 participants randomized into Cohorts 1 and 2, and their siblings (with the potential to collect a maximum of 33 if needed), at sites that have been trained and certified by the Sponsor/Sponsor designee to collect open muscle biopsies, following administration of anesthetic (eg, regional block or under general anesthesia) according to institutional standard practice, and only after any imaging and functional assessments scheduled for the same visit have been completed. Baseline Visit muscle biopsies will be performed after randomization. If a muscle biopsy cannot be scheduled on the day of the Baseline Visit, the biopsy may be performed at a later day, as long as it is at least 2 weeks before dosing.
- p. **Echocardiograms** will be collected and read locally for immediate interpretation and safety monitoring and will be submitted to a central laboratory for standardized interpretation.
- q. The **NSAA and CGIS** will be administered by a single clinical evaluator at each visit and whenever possible, the same CE should administer the functional assessments (NSAA, ankle range of motion and FVC) for the same participant throughout the study. The NSAA, ankle range of motion and FVC may be video recorded at the Day 1 (Screening Visit), Baseline Visit (Visit 2), and at the annual visits (ie, Visits 19, 35, 37, 39, 41, 43). If CE re-training is required, the assigned master physiotherapist may request additional visits to be recorded and reviewed. Whenever possible, motor functional assessments should be performed early in the course of the visit, to help reduce the effect of fatigue on the participants' performance; for additional advice regarding the ordering of assessments please consult the Functional Assessment Manual.
- r. **Ambulatory assessment** at Screening (Visit 1) is based only on the ability to perform the 10 m run/walk, as assessed during the NSAA.

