4.2.2. Rationale for Selected Participant Population

The selected population includes participants with a genetic diagnosis of DMD who are ambulatory and age ≥ 4 to < 8 years. There are two observations underlying the rationale for this age range.

The first, which defines the upper age limit, is based on the pathophysiology of DMD and the mechanism of action of fordadistrogene movaparvovec. Lack of functional dystrophin leads to damage of the sarcolemma upon repeated muscle contraction. This initially causes inflammation followed by cell death with replacement of muscle by fibrosis and fat. The goal of gene therapy is to provide mini-dystrophin to skeletal and cardiac muscle such that it replaces the missing or dysfunctional endogenous dystrophin and acts to protect muscle, thereby significantly reducing the inflammatory and fibrotic processes. Muscles that have already progressed to cell death and fibrosis are not expected to be affected by therapy. Thus, it is anticipated that maximum benefit will occur for patients in whom there is minimal irreversible muscle damage. Imaging studies have revealed that some inflammation and fibrosis occurs in select lower limb muscles in patients as early as age 2 years (Li et al., 2015).⁵¹ While most lower limb muscles have fatty infiltration by age 7 years, with the severity of fatty infiltration increasing rapidly after this age, different patients of the same age have varying degrees of fatty infiltration of the thigh muscles, ranging from mild to severe (Li et al., 2015).⁵¹ These imaging findings correspond to the average pace of clinical disease progression in which initial symptoms often present at age 2 years, improvement in ambulatory motor function occurs as a result of development through age 5 years, a plateau in function persists through age 7 years, and then decline occurs until loss of ambulation at approximately age 12 years (Ciafaloni et al., 2009; Bushby & Connor, 2011; McDonald et al., 2013; Mercuri et al., 2016).^{52,53,54,55} In order to minimize clinical heterogeneity and to treat boys prior to their anticipated functional decline, the designated age range for this trial has a maximum of <8 years old. However, as there is broad variability in DMD disease progression, and disease milestones will not occur at the same ages for all patients, there is the potential for treatment benefit outside of the age range included in the trial (Zambon et al., 2022; Bello et al., 2016)^{56,57}.

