5.1. Inclusion Criteria

Participants are eligible to be included in the study only if all of the following criteria apply:

1. Male participants who are ≥ 4 and < 8 years of age at Screening (Visit 1).
2. Confirmed diagnosis of DMD by prior genetic testing demonstrating the presence of a mutation in the dystrophin gene consistent with DMD at Screening (Visit 1). If the

Investigator determines that the results are inconclusive, a repeat genetic testing will be allowed through the central laboratory at Screening (Visit 1).

3. Receipt of a stable daily dose of glucocorticoids (≥ 0.5 mg/kg/day prednisone, prednisolone, or ≥ 0.75 mg/kg/day deflazacort) for at least 3 months prior to Screening (Visit 1) and during the period between Screening (Visit 1) and Day 1 (Visit 3). In order to comply with protocol procedures, there should also be a reasonable expectation that this daily dose of glucocorticoids will remain stable for the first 2 years of the study. A stable dose is defined as one in which any change is ≤ 0.2 mg/kg (See [Section 6.5.1](#) for detailed requirements).
4. A NSAA total score >16 and <30 at Screening (Visit 1).
5. Ambulatory, defined as being able to walk 10 meters unassisted, at Screening (Visit 1).
6. Participants/legally acceptable representatives who are willing and able to comply with all scheduled visits, treatment plan, laboratory tests, lifestyle considerations, and other study procedures including, potentially, open muscle biopsies under general anesthesia and cardiac MRI under general anesthesia.
7. Participants/legally acceptable representatives who are capable of giving assent/signed informed consent as described in [Appendix 1](#), which includes compliance with the requirements and restrictions listed in the assent/informed consent document (ICD) and in this protocol.
8. Participants/legally acceptable representatives who are willing to protect the integrity of the study data by not actively seeking sensitive clinical data (eg, CK, ALT, AST, NAb to AAV9) through independent laboratory tests and by not sharing trial experiences with other participants or publicly (eg, through social media).

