5.3.1. Study and Year 1 IP Administration Eligibility

If, due to operational or administrative reasons (eg, enrollment pause due to regulatory or safety review, operational issues causing significant delays), the time between the Screening Visit (Visit 1) and the Day 1 Visit (Visit 3), is more than 90 days, participants will undergo an unplanned visit to repeat the following tests and procedures, as applicable, and will re-confirm all study/IP administration eligibility criteria:

- Full physical and neurological examination;
- Vital signs;
- Laboratory tests: clinical safety, chemistry and hepatic safety, cardiac troponin, INR, and hepatitis serology;
- NAb to AAV9, if the previous sample was collected more than 55 days before the day of IP administration (see [Section 6.1.1](#));

- Functional assessments: NSAA, ambulatory status;
- Echocardiogram and ECG;
- Medical history, concomitant medications, and background glucocorticoid regimen assessment.
- Weight: for participants who were already randomized but have not yet received IP, weight will be measured again following the process outlined in [Section 8.2.3](#). The site will update the weight in the IRT system, to allow re-calculation of the dose of IP if needed, once study eligibility is re-confirmed. Participants with an increase or decrease in body weight of more than 5% will have the dose of IP re-calculated.

If a participant has started or completed the Screening Visit (Visit 1), but was not yet randomized when the assessments are repeated, and he is found to be ineligible for study entry based on the results of repeated tests and procedures, he will be screen failed.

If a participant was already randomized, but had not yet received IP when the assessments are repeated, and he is found to be ineligible for study entry based on the results of the repeated tests and procedures, he will be withdrawn from the study.

For participants who completed the Baseline Visit (Visit 2) and were randomized, and who are re-confirmed to be eligible for study entry, a second unplanned visit will be scheduled to perform a NAb to AAV9 test if the Day 1 Visit (Visit 3) is expected to be more than 55 days after the collection of the previous sample.

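### The primary MMRM leaves out the Screening NSAA score that every randomised boy has; the treatment difference stays unbiased, but a little precision is given up

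*Protocol*

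**What the plan says.** Protocol Sections 1.1 and 9.4.1 fix both the Baseline and the covariates of the primary model. Baseline is one value: "Baseline NSAA total score is defined as the last non-missing NSAA total score collected prior to Year 1 IP administration". Besides treatment, visit and their interaction, the fixed effects are "Baseline NSAA total score (continuous variable), Screening age (continuous variable), Baseline NSAA total score by visit interaction, and Screening age by visit interaction". The only Screening variable in the model is age.

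The Schedule of Activities (Section 1.3.1) marks the NSAA at both Visit 1 (Screening) and Visit 2 (Baseline). Criterion 4 in Section 5.1 makes the first of these an entry condition: "A NSAA total score >16 and <30 at Screening (Visit 1". Section 5 rules out prospective waivers of entry criteria, so every properly enrolled boy has a Screening total. If more than 90 days pass between Screening and dosing, Section 5.3.1 adds an unplanned visit that includes "Functional assessments: NSAA, ambulatory status".

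Section 9.4.1 analyses 10-metre run/walk and rise-from-floor velocity with a similar MMRM. These are the first two secondary endpoints in the testing order of Section 9.1. Section 9.5 uses the primary method unchanged at the optional looks at about 30 and 60 boys.

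**The concern.** The NSAA depends on effort and varies from day to day. The protocol acknowledges this by asking for early testing to limit fatigue, the same evaluator where possible, and ordinary activity for 24 hours beforehand. Short-term error in the last pre-dose score enters the change from Baseline with a negative sign. Adjusting for Baseline removes only part of it, because one score cannot separate a boy's true level from his error on that day. An earlier score on the same scale helps to separate them. It is measured before randomisation and already collected, yet it has no analysis role unless every later pre-dose score is missing.

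What is at stake is the width of the confidence interval for the primary treatment difference, and for the two velocity endpoints, in a trial of about 99 boys. The validity of the test is not in question. Section 9.4.1 leaves covariance structures and missing-data sensitivity analyses to the SAP but settles the covariates itself, so the choice belongs to the protocol.

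**Working it through.** **Inputs from the protocol.** Difference 3.0, common SD 3.5, 2:1 allocation, 99 boys less 3 dropouts, two-sided alpha 0.05 (Section 9.2), giving 64 and 32 evaluable. Screening total above 16 and below 30 (Section 5.1). Visit 1 on Day -90 to -30 and Visit 2 on Day -48 to -16 (Section 1.3.1).

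**Inputs assumed, because the protocol gives none.** Short-term NSAA SD s = 1.0, 1.5 or 2.0 points at each visit, independent between visits. True pre-dose SD 3.75 (variance V = 14.06). The 3.5 of Section 9.2 is taken as the SD of change (variance 12.25). Underlying change is independent of the true starting level.

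**Step 1: the plan's own power.** SE = 3.5 × √(1/64 + 1/32) = 0.758. Then 3.0/0.758 = 3.959, and Φ(3.959 − 1.960) = 97.7%. The plan says the sample "will provide 98% power to detect a treatment difference" of 3.0, so its figure reproduces. With gamma(−1) spending and looks at 30, 60 and 96 boys, cumulative power is 36.7%, 78.8% and 97.0%, against 38%, 78% and 97% stated.

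**Step 2: asymptotic gain.** Write Baseline B = T + e0, Screening S = T + es, and change C = D + e1 − e0. Then:

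- residual variance given B: 12.25 − s⁴/(V + s²)
- residual variance given B and S: 12.25 − s²(V + s²)/(2V + s²)

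| s | Given B | Given B and S | Variance falls | SE falls | Equivalent N (from 96) |
|---|---|---|---|---|---|
| 1.0 | 12.18 | 11.73 | 4% | 1.9% | about 100 |
| 1.5 | 11.94 | 11.04 | 7–8% | 3.8% | about 104 |
| 2.0 | 11.36 | 10.00 | 12% | 6.2% | about 109 |

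**Step 3: finite samples and eligibility.** The entry limits narrow the spread of Screening scores, and each extra covariate costs degrees of freedom and adds some chance imbalance. Simulating the Week 52 contrast with both features gives these changes in SE from adding Screening NSAA:

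| Boys | s = 1.0 | s = 1.5 | s = 2.0 |
|---|---|---|---|
| 96 | about −1% | about −2.5% | about −4.6% |
| 30 | about +0.4% | about −1.9% | about −3.2% |

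There was no bias with either model.

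**Step 4: a second parametrisation.** Take 3.5 as the residual SD with one baseline. Let ρ be the correlation of a pre-dose score with Week 52, and r the correlation between the two pre-dose scores. The residual variance is proportional to 1 − ρ² with one score and to 1 − 2ρ²/(1 + r) with two. At ρ = 0.7 and r = 0.85 to 0.90, the SE falls 4.0% to 2.6%. Over ρ = 0.5 to 0.8 and r = 0.75 to 0.95 it falls between 0.4% and 13.6%. A simulation with error SD 1.5 and a true difference of 3 gave mean estimates of 3.00 (Baseline only) and 2.99 (both scores). Empirical SEs were 0.766 and 0.743, a fall of 0.023/0.766 = 3.0%.

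**Step 5: effect on power.** Dividing 3.959 by 0.990, 0.975 and 0.954 (the 96-boy row of Step 3) and subtracting 1.960 gives 2.039, 2.101 and 2.190. Power becomes 97.9%, 98.2% and 98.6%, from 97.7%.

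**The case against.** The strongest reply is that nothing here is wrong. The last pre-dose value is a conventional baseline, the model is pre-specified and unbiased, and power is about 98%, so a further covariate is a matter of preference. Much of that stands. It limits the point to a minor improvement, though it does not remove a gain available from data already collected.

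Four stronger readings are tempting, and the documents do not support them.

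- *A reader might infer that error in Baseline distorts the treatment estimate.* It does not. The error falls alike on both randomised arms, and Baseline is itself a covariate with a visit interaction.
- *A reader might expect the gain to be largest at the small interim looks.* The calculation shows the reverse. At 30 boys the proportional gain is smallest, and it can vanish.
- *A reader might think the change is free.* It uses degrees of freedom: four coefficients per added covariate, one for each post-baseline NSAA visit.
- *A reader might take the age course in Section 4.2.2 ("improvement in ambulatory motor function occurs as a result of development through age 5 years, a plateau in function persists through age 7 years") as showing that a straight line in age is inadequate and that the age stratum must be added.* That passage describes an average course and gives no sizes. Continuous age by visit is already fitted, and in a simulation with no true age step the stratum term added no precision.

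It is also fair to object that the Screening score may be stale. The visit windows allow a gap of up to 74 days (Day -90 to Day -16), and a dosing pause can lengthen it. A longer gap weakens the prediction but introduces no bias, because the score still precedes randomisation.

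**Conclusion.** The point holds as a small loss of precision. The primary model omits a pre-randomisation measurement of its own outcome that every randomised boy has. Including it would lower the SE at 96 boys by roughly 1% to 5%, or 2% to 6% asymptotically, and raise power by about one percentage point or less from 97.7%. These figures rest on an assumed short-term SD of 1.0 to 2.0 points and a true pre-dose SD of 3.75. The protocol supplies neither, and the wider correlation grid shows that the gain could be smaller or larger. No size was computed for the two velocity endpoints. The SAP was not available for this check. The point is minor: it touches neither the validity of the primary test nor the adequacy of the sample size.

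**What to change.** Before any unblinding, including for an interim look, add two fixed effects to the primary MMRM in Sections 1.1 and 9.4.1: the Visit 1 Screening NSAA total score (continuous) and its interaction with visit. Leave the endpoint and the Baseline definition as they are. In the 10-metre run/walk and rise-from-floor velocity models, add the Visit 1 value of each measure in the same way; both times are recorded as part of the NSAA (Section 8.1.1).

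Name the score to be used: the original Visit 1 value, even when the NSAA is repeated after a dosing pause under Section 5.3.1. The repeated score may then serve as Baseline under the existing definition.

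The cost is a short text change, carried into the SAP. Because Section 9 requires major changes to the primary analysis to appear in a protocol amendment, it should go into the next one. Statistically it costs a few degrees of freedom, with little or no benefit at a 30-boy look. The sample size need not change.
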